8.3.5 Disease-Related Events and/or Disease-Related Outcomes Not Qualifying as AEs or SAEs

DREs and/or DROs should not be reported to the Global safety database.

The following DREs are common in participants with malaria and can be serious/ life-threatening:

- Severe *P.falciparum* malaria, is defined as ≥ 1 of the following, occurring in the absence of an identified alternative cause and in the presence of *P.falciparum* asexual parasitemia.
 - Impaired consciousness: A Glasgow coma score < 11 in adults or a Blantyre coma score < 3 in children.
 - Prostration: Generalized weakness so that the person is unable to sit, stand, or walk without assistance.
 - Multiple convulsions: > 2 episodes within 24 hours.
 - Acidosis: A base deficit of > 8 mEq/L or, if not available, a plasma bicarbonate level of < 15 mmol/L or venous plasma lactate ≥ 5 mmol/L. Severe acidosis manifests clinically as respiratory distress (rapid, deep, labored breathing).
 - Hypoglycemia: Blood or plasma glucose < 2.2 mmol/L (< 40 mg/dL).
 - Severe malarial anemia: Hb concentration ≤ 5 g/dL or a hematocrit of $\leq 15\%$ in children < 12 years of age (< 7 g/dL and $< 20\%$, respectively, in adults) with a parasite count $> 10,000/\mu\text{L}$.

- Renal impairment: Plasma or serum creatinine $> 265 \mu\text{mol/L}$ (3 mg/dL) or blood urea $> 20 \text{ mmol/L}$.
- Jaundice: Plasma or serum bilirubin $> 50 \mu\text{mol/L}$ (3 mg/dL) with a parasite count $> 100,000/\mu\text{L}$.
- Pulmonary edema: Radiologically confirmed or oxygen saturation $< 92\%$ on room air with a respiratory rate $> 30/\text{min}$, often with chest indrawing and crepitations on auscultation.
- Significant bleeding: Including recurrent or prolonged bleeding from the nose, gums, or venipuncture sites; hematemesis or melena.
- Shock: Compensated shock is defined as capillary refill $\geq 3\text{s}$ or temperature gradient on leg (mid to proximal limb), but no hypotension. Decompensated shock is defined as SBP $< 70 \text{ mmHg}$ in children or $< 80 \text{ mmHg}$ in adults, with evidence of impaired perfusion (cool peripheries or prolonged capillary refill).
- Hyperparasitemia: *P. falciparum* parasitemia $> 10\%$.

Because these events are typically associated with the disease under study, they will not be reported according to the standard process for expedited reporting of SAEs even though the event may meet the definition of a SAE. These events will be recorded within 24 hours.

However, if either of the following conditions applies, then the event will be recorded and reported as an AE/SAE (instead of a DRE):

- The event is, in the Investigator's opinion, of greater intensity, frequency, or duration than expected for the individual participant.

OR

- The Investigator considers that there is a reasonable possibility that the event was related to study intervention.

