Utilization of an active control cohort consisting of either SPAQ or any other ACTs would not be appropriate at the current stage of clinical development as these drug combinations would all provide protection over 3 weeks against recurrent infections. The currently available data are not sufficient to support repeated M5717 plus pyronaridine dose regimens; indeed, definition of the dose regimen is the purpose of the current study.

CCI

The study population of adults and adolescents has been selected based on the expected safety profile of the M5717 plus pyronaridine

combination as well as the safety profile of M5717 in healthy volunteers. Pyronaridine is approved for children weighing ≥ 20 kg and adults in combination with artesunate (Pyramax SmPC). Safety of adults and adolescents will be ensured by multiple risk mitigation measures (e.g. safety monitoring, entry criteria, DMC, predefined AESIs). It is well known that over time malaria patients develop protective immunity, and the risk of clinical malaria decreases with age. Severe malaria, at least in countries where transmission is moderate, is extremely rare in adolescents and adults.

[figure not shown]
The study interventions M5717 and pyronaridine will be administered as single doses based on the long-lasting activity of the M5717-pyronaridine combination, thereby potentially improving the dosing regimen currently considered as standard of care for SMC, which currently requires a 3-day treatment.

[figure not shown]
The scientific rationale for the substudy is provided in [Appendix 2](#).

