8.3.6 Adverse Events of Special Interest

Liver events (AT increase, TB increase) and CNS events will be considered AESIs and specifically followed-up through laboratory surveillance and a specific physical examination at specific visits during the follow-up. All those events should be reported to the Sponsor within 24 hours of knowledge and appropriate updates should be provided when new information becomes available.

For this study, AESI(s) include only the following:

- Liver events will be monitored through LFTs that will include the 2 ATs, ALT, and AST, as well as TB and ALP. Specific details regarding the values confirmation, follow-up, and monitoring frequency are provided in [Appendix 6](#).
- Neurological events will be monitored through specific neurological clinical examinations, detailed in [Section 8.2.1](#). This neurological physical examination will be done at Screening and at every visit. If additional tests or assessments (such as CT, MRI, lumbar puncture) are required to further evaluate neurological abnormalities detected, those will be done at the discretion of the Investigator.

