If death occurs, the primary cause of death or event leading to death will be recorded and reported as an SAE. “Fatal” will be recorded as the outcome of this specific event and death will not be recorded as separate event. Only, if no cause of death can be reported (e.g. sudden death, unexplained death), the death per se might then be reported as an SAE.

Assessment of Causality

- The Investigator will assess the relationship between study intervention and each AE/SAE occurrence:
 - Unrelated: Not reasonably related to the study intervention. AE could not medically (pharmacologically/clinically) be attributed to the study intervention. A reasonable alternative explanation will be available.
 - Related: Reasonably related to the study intervention. AE could medically (pharmacologically/clinically) be attributed to the study intervention.
- A “reasonable possibility” of a relationship conveys that there are facts, evidence, and/or arguments to suggest a causal relationship, rather than a relationship cannot be ruled out.
- The Investigator will use clinical judgment to determine the relationship.
- Alternative causes, such as underlying disease(s), concomitant therapy, and other risk factors, as well as the temporal relationship of the event to study intervention administration will be considered and investigated.
- The Investigator will also consult the IB and/or Product Information, for marketed products, in his/her assessment.
- For each AE/SAE, the Investigator will document in the medical notes that he/she has reviewed the AE/SAE and assessed causality.
- There may be situations when an SAE has occurred, and the Investigator has minimal information to include in the initial report to the Sponsor or its designee. To meet the reporting timeline, the causality assessment is not required for the initial report.
- The Investigator may change his/her causality assessment after considering follow-up information and send an SAE follow-up report with the updated causality assessment.
- The causality assessment is one of the criteria used when determining regulatory reporting requirements.

Follow-up of AEs and SAEs

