- **Death due to malaria or other reasons:** filter SAEs programmatically for fatal events with outcome "death" and by medical/safety review. Death cases for which the primary reason is ticked as "progressive disease and/or disease-related condition" qualify as death due to malaria. A composite variable strategy is applied if the death was due to malaria (i.e. a parasitemia event is considered at the time of death) and an on-treatment strategy is defined if death was due to other reasons (i.e. time to parasitemia is censored at the time of death)

The population-level summary is defined as the Hazard Ratios (HRs) for each dose of M5717 relative to the untreated participants in Cohort 4. HRs are estimated from a Cox Proportional Hazards Model with time to parasitemia included as the dependent variable and dose cohorts, site and sex included as independent factors, and baseline age, body weight and parasite density included as independent covariates. Participants will be censored in case of occurrence of an ICE as described above, at the last available visit in case of premature study discontinuation or at the end of study in case no parasitemia event was observed.

For the multivariable (primary) model, a table showing HRs together with 95% Wald CIs will be provided which will contain in addition estimates of coefficients, SEs and p-values (based on Likelihood Ratio Test) in order to assess whether the factors and covariates included into the model have a significant influence on the time to parasitemia. As additional information a table providing information on censoring frequency and occurrence of ICEs will be provided.

As part of descriptive analyses of the primary endpoint, which also covers the analysis of the second estimand (incidence of parasitemia), a table displaying number and percentages of

parasitemia events (estimated directly from the data) will be provided together with estimates of a Kaplan-Meier (KM) analysis. Median time of protection and 95% CI will be estimated using the KM method for each cohort. As a graphical illustration, a KM-figure will be provided showing time to parasitemia in days after parasite clearance.

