15.2.4 Disease Related Events

Disease related events are captured separately in the same manner as Adverse Events. They will be separated by the time of their occurrence, i.e. events with onset or worsening dates on or after the first administration of study intervention and events with onset or worsening dates before the first administration of study intervention. Frequency tables displaying incidences of disease related events will be provided by SOC and PT separately for events occurring before and after study intervention as defined above.

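### Protocol 8.3.5 makes severe-malaria CNS events disease-related events by default, 8.3.6 makes all CNS events AESIs, no rule of precedence is given, and the SAP's AESI and Tier 1 tables count AEs only

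*Protocol*

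**What the plan says.** Protocol 8.3.5 is headed "Disease-Related Events and/or Disease-Related Outcomes Not Qualifying as AEs or SAEs". It lists 12 severe-malaria criteria, each requiring *P. falciparum* asexual parasitaemia and no identified alternative cause. Among them are a coma score below a cut-off, "Multiple convulsions: > 2 episodes within 24 hours", and jaundice (bilirubin above 50 µmol/L with more than 100,000 parasites/µL). The section states that "DREs and/or DROs should not be reported to the Global safety database" and exempts these events from the standard expedited SAE process, although they are recorded within 24 hours. An event returns to AE/SAE status on either of two investigator judgements: that it is worse than expected for that participant, or that a relation to study intervention is reasonably possible.

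Protocol 8.3.6 makes liver events (aminotransferase or bilirubin increase) and CNS events AESIs, and adds: "All those events should be reported to the Sponsor within 24 hours of knowledge". Protocol 9.4.2 repeats the AESI rule. Neither section has an exception for DREs.

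SAP 15.1 defines AESIs as AEs ticked as such on the AE form, plus AEs found by a list of preferred terms. SAP 15.1.2 makes the Nervous system disorders SOC a Tier 1 category, with a rate difference and 95% CI for each dose cohort against the natural infection cohort. SAP 15.2.4 says: "Disease related events are captured separately in the same manner as Adverse Events". It gives DREs their own tables by SOC and preferred term, before and after study intervention.

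**The concern.** Coma or repeated convulsions in a parasitaemic participant fall under two rules that give different instructions. Under 8.3.6 the event is an AESI, due to the sponsor within 24 hours. Under 8.3.5 it is by default not an AE at all.

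The parasitaemia condition is easily met. Inclusion criterion 2 requires 40 to 10,000 asexual parasites/µL, so every participant satisfies it at dosing and until clearance. That is the period just after the single M5717 dose, when a drug-related CNS event would be of interest.

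CNS is one of two event types that the protocol singles out as AESIs, and it has its own stopping criteria. If an investigator who knows the cohort decides whether an event is a DRE or an AE, the Tier 1 nervous-system comparison depends on that attribution. The AE tables of a named risk should not.

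**Working it through.** This is mainly a cross-reading. The only arithmetic is for scale.

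1. **Overlap of the two lists.** Of the 12 DRE criteria, two are plainly CNS (impaired consciousness, multiple convulsions). One is a bilirubin criterion. Prostration is defined as generalised weakness and is not clearly neurological, so it is not counted. The clear overlap is 3 of 12.

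2. **Liver part.** No aminotransferase criterion is on the DRE list, so aminotransferase rises stay AEs and AESIs. The bilirubin criterion needs more than 100,000 parasites/µL, which is 100,000 / 10,000 = 10 times the entry maximum. The laboratory tables, shift tables and eDISH plot in SAP 15.2.5 have no stated DRE exclusion, so the values stay visible.

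3. **What remains a DRE.** After both return conditions in 8.3.5, the events left are those judged within expectation and without a reasonable possibility of relation to study intervention. Appendix 5 says that a reasonable possibility needs facts, evidence or arguments, and that being unable to rule a relation out is not enough. An ambiguous early event can therefore stay a DRE.

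4. **Consequence in the SAP.** AESI and Tier 1 counts come from AEs, and DREs are held separately. An event left as a DRE is in the SAP 15.2.4 table but in neither the AESI table nor the Tier 1 difference.

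5. **Scale.** 192 randomised / 4 cohorts = 48 per cohort. One event is 1/48 = 2.1 percentage points. SAP 15.1.2 suppresses the interval for Tier 1 events seen in fewer than 3 participants. In a row with exactly 3 participants, leaving one as a DRE gives 3 − 1 = 2 and removes the interval. These are illustrations, not expected counts. Protocol 4.2 says: "Severe malaria, at least in countries where transmission is moderate, is extremely rare in adolescents and adults".

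6. **Malaria deaths.** Appendix 5 says in its SAE definition that an event which is not an AE cannot be an SAE, with death from disease progression as an example. The same appendix later says: "If death occurs, the primary cause of death or event leading to death will be recorded and reported as an SAE". SAP 14.1.1 looks for deaths with an instruction to "filter SAEs programmatically for fatal events with outcome" of death, adding medical/safety review. It does not name the DEATH form (SAP 15.2.1) or the DRE data as sources.

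**The case against.** The strongest reply is that the rules can be read together. In the SAP an AESI is by definition an AE, and a DRE is by definition not one. Moreover, 8.3.5 concerns the global safety database, whereas 8.3.6 concerns reporting to the sponsor. This does not settle the matter. Appendix 5 sends a serious AESI through the SAE form and process, which is the route that 8.3.5 closes, and 8.3.6 allows no exception. If the narrower reading is intended, the protocol must say so.

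The second reply is that few events would stay DREs. Participants are asymptomatic, afebrile and at low parasite density, so coma or repeated convulsions would readily count as worse than expected. Appendix 5 also reports clinical sequelae of lack of efficacy as AEs or SAEs if they meet the definition. This stands, and it keeps the point small. The outcome still rests on opinion in an open-label study.

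Three stronger readings are tempting, and the documents do not support them:

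- **That DREs vanish from the data.** They are recorded within 24 hours and tabulated by SOC and preferred term.
- **That the study hold can be bypassed.** The CNS stopping criteria in protocol 4.1 cover only intervention-related events, and any event with a reasonable possibility of relation returns to AE/SAE. Only the investigator's judgement of relatedness remains, and the fix would not change that.
- **That malaria deaths would be lost from the primary endpoint.** A severe-malaria DRE requires parasitaemia. If the smear never cleared, SAP 14.1.1 leaves the participant out of the analysis. If parasitaemia recurred, the positive smear is already the event, and rescue medication also counts as failure. Medical review is a further safeguard.

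**Conclusion.** The contradiction is real and should be resolved. Protocol 8.3.5 takes coma, multiple convulsions and one high-parasitaemia bilirubin criterion out of AE/SAE reporting by default, 8.3.6 and 9.4.2 make such events AESIs without exception, and nothing gives precedence. Because the SAP counts AESIs and Tier 1 events from AEs only, an event left as a DRE is missing from the nervous-system comparison with Cohort 4 on open-label judgement.

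The expected effect is very small: few such events, each worth 2.1 points in a cohort of 48, in a study whose analyses are all descriptive. The direction of any bias cannot be stated. The liver overlap is remote, and the conflict over malaria deaths is a minor consistency point.

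This assumes that sites apply 8.3.5 as written, that coma and convulsions would be coded to the Nervous system disorders SOC, and that the SAP term list is applied to AE data only, as SAP 15.1 says.

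**What to change.** **Protocol 8.3.5 and 8.3.6:** add one precedence sentence saying that an event which meets the AESI definition is also recorded and reported as an AESI whatever its attribution, even if it meets a severe-malaria criterion. The DRE category can stay for all other events.

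**SAP 15.1.2 and 15.2.3:** count post-dose DREs whose terms are on the AESI list or in the Nervous system disorders SOC, or show them pooled with the AESIs by cohort. Appendix 5 prefers a diagnosis to individual signs, so a convulsion might be entered only as severe malaria. The DRE record should therefore also hold the criterion that was met, or a search by term will miss it.

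**Minor consistency:** reconcile the two Appendix 5 statements on deaths, and in SAP 14.1.1 name the DEATH form and the DRE data as sources alongside SAEs.

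**Cost:** wording in both documents and some programming, since DREs are already coded by SOC and preferred term. The downside is a few extra AESI reports for events that turn out to be malaria.

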8.3.6 Adverse Events of Special Interest

Liver events (AT increase, TB increase) and CNS events will be considered AESIs and specifically followed-up through laboratory surveillance and a specific physical examination at specific visits during the follow-up. All those events should be reported to the Sponsor within 24 hours of knowledge and appropriate updates should be provided when new information becomes available.

For this study, AESI(s) include only the following:

- Liver events will be monitored through LFTs that will include the 2 ATs, ALT, and AST, as well as TB and ALP. Specific details regarding the values confirmation, follow-up, and monitoring frequency are provided in [Appendix 6](#).
- Neurological events will be monitored through specific neurological clinical examinations, detailed in [Section 8.2.1](#). This neurological physical examination will be done at Screening and at every visit. If additional tests or assessments (such as CT, MRI, lumbar puncture) are required to further evaluate neurological abnormalities detected, those will be done at the discretion of the Investigator.

8.4 Pharmacokinetics

8.4.1 Blood Sampling and Bioanalysis

PK sampling timepoints are provided in the SoA (Section 1.3). Blood samples will be taken for participants randomized to Cohorts 1 to 3 during the dosing day (Day 1, Visit 1) and at each subsequent visit to assess the PK of M5717 and pyronaridine. The exact sampling timepoints at Day 1 to 2 (24 hour sampling after dosing) are provided in Table 2.

- Samples are collected only where allowed by local law/regulations.
- The actual date and time (24 hour clock time) of:
 - Each sample collection
 - Study intervention administration prior to sample collection

will be recorded in the eCRF to determine the elapsed time of sampling in relation to the administration of study intervention.

- Additional samples may be collected during the study if warranted and agreed upon between the Investigator and the Sponsor. The sampling timing may be altered during the study based on newly available data (e.g. to obtain data closer to the time of peak plasma concentrations) to ensure appropriate monitoring.
- The quantification of M5717 and pyronaridine in whole blood will be performed using validated assay methods. Concentrations will be used to evaluate the PK of M5717 and pyronaridine.
- Remaining samples collected for bioanalytical measurements may also be used for evaluation of safety or efficacy aspects related to concerns arising during or after the study, CCI [REDACTED] of metabolites of study intervention, or CCI [REDACTED] during or after the study. Retention time and possible analyses of samples after the end of study are specified in the respective ICF.
- Details on processes for collection and handling of these samples are in the Laboratory Manual. Retention time and possible analyses of samples after the end of study are specified in the respective ICF.

8.4.2 PK Parameters

The following PK parameters for M5717 and pyronaridine will be calculated, when appropriate:

Symbol	Definition
AUC _{0-∞}	The AUC from time zero (= dosing time) up to infinity with extrapolation of the terminal phase.
CL/F	The apparent total body clearance following extravascular administration.
C _{max}	Maximum observed concentration.
t _{1/2}	Apparent terminal half-life. t _{1/2} = ln (2)/λ _z .
t _{max}	The time to reach the C _{max} in a dosing interval.
V _z /F	The apparent volume of distribution during the terminal phase following extravascular administration.

Symbol	Definition
$AUC_{0-t_{last}}$	The AUC from time zero (= dosing time) to the time of the last quantifiable concentration (t_{last}).
$AUC_{0-t_{last}}/\text{Dose}$	The dose normalized $AUC_{0-t_{last}}$.
$AUC_{0-\infty}/\text{Dose}$	The dose normalized $AUC_{0-\infty}$.
C_{\max}/Dose	The dose normalized C_{\max} .

Other PK parameters might be added based on emerging data. Details will be provided in the IAP.

Details on PK sampling for M5717 and pyronaridine are provided in Section 8.4.1.

Concentration data may be used for integrated data analyses across studies, such as population PK and exposure response analyses of PD biomarker, efficacy, and/or safety analyses and reported separately from the main CSR.

CCI

1

Horizontal bar chart showing CCI values for various categories. The y-axis is labeled "Category" and the x-axis is labeled "CCI" with a scale from 0 to 100. The chart shows 10 categories with CCI values ranging from approximately 10 to 95.

Category	CCI
1	95
2	10
3	10
4	10
5	10
6	10
7	10
8	10
9	10
10	10

8.7 Immunogenicity Assessments

Not applicable.

8.8 Medical Resource Utilization and Health Economics

Healthcare resource utilization data are not collected in this study.

9 Statistical Considerations

Details of the analysis of efficacy, safety, and PK will be presented in the IAP, which will be finalized before the database is locked for analysis.

Statistical considerations for the DMFA substudy are provided in [Appendix 2](#).

